7.9.3.5 Patient preference

To characterize the Patient preference of DBS mode.

Endpoint definition

Patient preference for DBS modes will be assessed by the Patient preference questionnaire at the screening Visit and at the end of the aDBS treatment phase.

Analysis methods

The Patient preference questionnaire assesses subject preference for DBS modes on two items: disease-related symptoms (shaking, slowness, stiffness) and any side effects (trouble swallowing, change in mood, tingling). At screening, subjects will reply that they prefer the single threshold, double threshold, no preference, or do not know. At Visit 3, subjects will reply that they prefer the DBS mode received during period A, the DBS mode received during period B, no preference, or do not know. The responses will be summarized as categorical measures.

7.9.3.6 LFP dynamics

To characterize the LFP dynamics based on out of clinic patient event markers and PD Medication cycle

Endpoint definition

LFP will be recorded through Rune Labs database.

Analysis methods

Subjects may choose to participate in optional data collection of Events with LFP capture (snapshots). The clinician may set up a maximum of 4 event types, selected from the following options: dyskinesia, tremor, rigidity, freezing, sleep disturbance, took PD medication.

7.9.3.7 Percept Device and Apple Watch

To assess correlation among movement and sleep data collected from Apple Watch, Percept Device data and clinical measures.

Endpoint definition

Percept Device data, Apple Watch data and clinical outcomes (GIC, PDQ-39 SI, MDS-UPDRS III, UDysRS and EQ-5D-5L). Percept Device and Apple Watch data will be provided by Rune Labs (see Appendix A).

Analysis methods

The parameters summarized with the device data from Percept Device and Apple Watch are listed in Appendix A. Summary statistic will be reported in aDBS, cDBS and by aDBS preferred mode. Correlations will be assessed visually as appropriate.

7.9.3.8 Patient Satisfaction

To assess Patient satisfaction with aDBS (preferred mode).

Endpoint definition

Patient satisfaction questionnaire

Analysis methods

The patient satisfaction questionnaire will assess the overall satisfaction and satisfaction on specific items on 5 levels of satisfaction (very satisfied, somewhat satisfied, neutral, somewhat unsatisfied and very unsatisfied) and by the recommendation of adaptive DBS to other DBS patients with Parkinson's Disease. The responses will be summarized as categorical measures only for aDBS mode (any preferred mode).

7.9.3.9 Global Impression of changes

To assess Global Impression of changes (GIC) with aDBS (preferred mode).

Endpoint definition

DBS Global Impression of Change score (DBS GIC)

Analysis methods

GIC scores can be used to help assess for acceptability of aDBS for an individual subject. A lower number is better in terms of acceptability (ie, greater efficacy with minimal side effects). The responses will be summarized as categorical measures.

7.10 Safety Evaluation

All reportable adverse events (AEs) and all device deficiencies (DDs) will be collected throughout the study once the informed consent form is signed. The safety evaluation will be performed on the all screened subjects or as treated (AT) set as appropriate and presented with summary tables and supporting data listings.

AEs and DDs will be coded and summarized using the Medical Dictionary for Regulatory Affairs (MedDRA). Summaries include the number of events, the number of subjects who experience an event, and the percentage of subjects who experienced one or more events. The denominator will include the

appropriate number of subjects for each respective phase and period. In particular, the following objectives will be reported separately:

- Stimulation-related adverse events during the aDBS treatment Phase.
- Serious adverse events which occur through the study after consent and which causal relationship with Percept PC cannot be ruled out.
- Any-cause death throughout the study after Screening Visit starts.
- Device (Percept PC) deficiencies that involves or potentially involves a serious adverse event throughout the study after the randomization.

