11.2 Device Deficiency

The following Device Deficiency (DD) will be collected for safety analyses in this study

- Device (Percept PC) deficiencies that potentially could have led to a serious adverse event

DDs that did not lead to a serious adverse event but could have led to a serious adverse device effect include the following

- if either suitable action had not been taken
- if intervention had not been made
- if circumstances had been less fortunate

The DD definition is provided in Table 2. Reportable DD information will be collected throughout the study after signing the IC and reported to Medtronic on the DD eCRF. Note that DD that result in an AE to the subject should be captured as an AE only.

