12.6 Safety Assessment

To assess safety in following items:

- Stimulation-related adverse events during the aDBS treatment phase.

- Serious adverse events which occur through the study after consent and for which the relationship with Percept PC cannot be ruled out.
- Any-cause death throughout the study.
- Device (Percept PC) deficiencies that potentially involve a serious adverse event throughout the study: for all subjects

Stimulation-related adverse events will be summarized during the aDBS treatment phase for all subjects, with listings individualized by aDBS mode and cDBS.

Serious adverse events, adverse events, and device deficiencies that occur from the consent through study exit/discontinuation will be summarized for all enrolled subjects. The denominator will include the appropriate number of subjects for each respective phase and period. Events will be summarized by number of events, number of subjects who experienced the event, and percentage of subjects who experienced the event.

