4.3 Safety assessment

To assess safety in the following items:

- Stimulation-related adverse events during the aDBS treatment phase
- Serious adverse events which occur through the study after consent and for which the relationship with Percept PC cannot be ruled out: for all subjects
- Any-cause of death throughout the study: for all subjects.
- Device (Percept PC) deficiencies that potentially involve a serious adverse event throughout the study: for all subjects

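### SAP 7.10 starts the separately reported device-deficiency and death objectives later than SAP 4.3 and the protocol do

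*SAP*

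**What the plan says.** SAP 7.10 lists four safety objectives to be reported separately. Three of them name a starting event, and each names a different one:

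- Serious adverse events start at consent: "Serious adverse events which occur through the study after consent and which causal relationship with Percept PC cannot be ruled out".
- Deaths start at a screening visit: "Any-cause death throughout the study after Screening Visit starts".
- Device deficiencies start at randomization: "deficiencies that involves or potentially involves a serious adverse event throughout the study after the randomization".

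The fourth, stimulation-related events, is confined to the aDBS treatment phase in both documents and is not at issue.

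The same section opens with a collection rule that starts at consent: "All reportable adverse events (AEs) and all device deficiencies (DDs) will be collected throughout the study once the informed consent form is signed". It also plans general summaries, with no start date: "AEs and DDs will be coded and summarized using the Medical Dictionary for Regulatory Affairs (MedDRA".

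SAP 4.3 states the deficiency objective without any later start: "deficiencies that potentially involve a serious adverse event throughout the study: for all subjects". It treats any-cause death in the same way, and protocol 4.1.3 agrees on both. Protocol 12.6 gives the analysis rule: "Serious adverse events, adverse events, and device deficiencies that occur from the consent through study exit/discontinuation will be summarized for all enrolled subjects". Protocol 11.2 collects deficiencies once consent is signed and adds: "Note that DD that result in an AE to the subject should be captured as an AE only".

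**The concern.** Two of the four pre-specified safety objectives have a start in SAP 7.10 that disagrees with the protocol and with the SAP's own statement of objectives. A programmer who follows SAP 7.10 literally would leave the following out of the separate lines:

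- any deficiency before randomization;
- any deficiency in a subject who consents but is never randomized, for example one who fails eligibility at Baseline;
- any death before the undefined screening visit.

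The device can be in active use during this time. Under protocol 9.6 the signal test may be run, LFP thresholds are set if not already set, and subjects who arrive on aDBS are switched to cDBS for washout. These steps are conditional, so they apply to some subjects and not to all.

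Protocol 12.2 says that a departure from the planned methods will be documented in the SAP with its statistical rationale. SAP 7.10 gives none, so the later starts read as unreconciled wording and not as a deliberate choice.

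**Working it through.** The documents give no figure on this point to reproduce. The check compares the start points and then bounds the gap from the visit windows.

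**1. Start points compared**

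| Source | Device deficiencies | Any-cause death |
|---|---|---|
| Protocol 4.1.3 | whole study, all subjects | whole study, all subjects |
| Protocol 11.1 and 11.2 (collection) | from signed consent | from signed consent |
| Protocol 12.6 | consent to exit, all enrolled | whole study |
| SAP 4.3 | whole study, all subjects | whole study, all subjects |
| SAP 7.10, opening sentence (collection) | from signed consent | no separate statement |
| SAP 7.10, separate objectives | after randomization | after a 'Screening Visit' |

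Only the last row starts later. In protocol 4.1.3 and SAP 4.3 the consent wording is attached to the serious-event item alone. The explicit consent start for deficiencies comes from protocol 12.6 and 11.2.

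**2. Meaning of 'Screening Visit'**

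Neither visit schedule (protocol Table 1, SAP Figure 5-2) has such a visit. The protocol synopsis and 9.6 place screening at Baseline. SAP 7.9.3.5 uses the term for the preference questionnaire, which the schedule places at Baseline. Protocol 10.1.2 uses it loosely as well. Baseline is the likely meaning, and it is an assumption below.

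**3. Length of the gap**

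Inputs:
- Consent to Baseline: 0 days (same day allowed, protocol 9.5) to 30 days (9.6).
- Baseline to randomization: 0 days if the subject has been on cDBS for at least 7 days (9.6), at least 7 days if washout starts at Baseline, and at most 30 days (9.7).

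Gap in the deficiency line = (consent to Baseline) + (Baseline to randomization):
- Minimum: 0 + 0 = 0 days.
- Minimum when washout starts at Baseline: 0 + 7 = 7 days.
- Maximum: 30 + 30 = 60 days.

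Gap in the death line = consent to Baseline = 0 to 30 days, if 'Screening Visit' means Baseline.

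**4. Share of participation**

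Longest in-window schedule: 60 days to randomization, two periods of 45 + 7 = 52 days, and three follow-up intervals of 60 + 7 = 67 days.

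60 + 2 × 52 + 3 × 67 = 60 + 104 + 201 = 365 days

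This agrees with the participation of about 12 months in protocol 5.1. The maximum share is then 60 / 365 = 16%.

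With nominal 45-day periods and 60-day follow-up intervals the total is 60 + 2 × 45 + 3 × 60 = 330 days, and the share is 60 / 330 = 18%. The share rises further for a subject who exits early, so the 60-day ceiling is the firmer figure.

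**5. What the other SAP 7.10 outputs still capture**

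- A serious event whose relation to Percept PC cannot be ruled out is reported from consent. A fatal one before Baseline would appear there.
- A deficiency that results in an adverse event is recorded as an adverse event under protocol 11.2.
- What can be missing from the separate lines is therefore narrow: deficiencies before randomization with the potential for a serious event but no resulting adverse event, and deaths before screening. Of those deaths, the ones judged unrelated to Percept PC would be in neither the death line nor the serious-event line.

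**The case against.** The strongest defence is that little need be lost. SAP 7.10 collects all reportable adverse events and all deficiencies from consent and plans coded summaries and supporting listings with no randomization limit. It also allows all screened subjects as a safety population. The list is introduced as a set of items to be shown separately, so an early deficiency could miss one line and still appear elsewhere. Under protocol 11.7 a death is also entered on the adverse event and study exit forms. The window can be zero days, and a subject who fails eligibility leaves at Baseline with no further study procedures.

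Most of this stands, and it limits the point. A reader might infer that early safety events vanish from the report. The documents do not support that, given the general summaries and listings and the consent start for related serious events. A reader might also take 60 days as the usual gap, but it is a ceiling.

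A reader might further infer double counting, because the SAP item covers deficiencies that involve a serious event as well as those that could. Protocol 11.2 makes this unlikely: such a deficiency is recorded only as an adverse event, so no deficiency record should exist to be counted again. The wording is at most redundant.

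The defence does not remove the contradiction. The separate lines are how the SAP reports the pre-specified objectives, and two of them have starts that disagree with protocol 4.1.3 and SAP 4.3. The option of all screened subjects does not settle it either: SAP 7.1.3 does not define that set, and the after-randomization limit on the deficiency item would still apply.

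**Conclusion.** The start points for two separately reported safety objectives in SAP 7.10 are wrong as written. They contradict SAP 4.3 and protocol 4.1.3, and for deficiencies also protocol 12.6 and 11.2.

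- **Deficiency line:** omits 0 to 60 days per subject, at most about 16% of a 365-day participation, and all deficiencies in enrolled subjects who are never randomized.
- **Death line:** omits 0 to 30 days per subject, on the assumption that 'Screening Visit' means Baseline.

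The number of events affected cannot be estimated from the documents. The omission concerns the separate objective lines and does not establish a loss from the whole report. These objectives are descriptive, so the hypotheses, sample size, power and alpha are unaffected. The correction is worth making because it concerns pre-specified safety objectives and the data are already collected.

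**What to change.** In the SAP 7.10 list, replace the after-randomization limit on the deficiency item and the screening-visit limit on the death item with the same words: *from informed consent through study exit, for all enrolled subjects*. This also removes the undefined visit name from that section.

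As a minor consistency edit, word the deficiency item to match protocol 11.2: deficiencies that could have led to a serious event, with any deficiency that results in an adverse event reported as an adverse event only.

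The cost is two replaced phrases and one small wording change in the SAP. No new data are needed, because both documents already require collection from consent. If the sponsor does intend the later starts, the SAP should give the rationale that protocol 12.2 calls for, define the screening visit, and reconcile SAP 4.3 with SAP 7.10.

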7.11 Changes to Planned Analysis

Any change to the data analysis methods described in the SAP will require an amendment only if it changes a principal feature of the SAP. Any other change to the data analysis methods described in the SAP, and the justification for making the change, will be described in the clinical study report.

8. Validation Requirements

All collected data will be reviewed for completeness correctness and consistency. In case of issues, queries will be sent to the investigator to complete, correct or comment the data. Statistical programming code that affects the result of the main analysis (e.g., not including sensitivity or supporting analyses) for the primary objective shall be validated using Level I validation. Programming code for randomization and programming code that affects the result of the main analysis for the secondary objective(s) shall be validated using at least Level II validation. In addition, those main statistical analyses that are planned for publication and have not been previously validated should be validated using at least Level II validation. The CIP deviation summary shall be validated using at least Level III validation and the high-level adverse event summary shall be validated using at least Level II validation. Additional measures where a p-value or confidence interval has been generated may need to be validated using at least Level II validation.

9. References

1. Simon Little, MA, MBBS, [name], Spencer Neal, BEng (Hons), Baltazar Zavala, BA, [name], [name], et al. Adaptive Deep Brain Stimulation in Advanced Parkinson Disease. Little et al. 2013;74(3):449-457.
2. Simon Little, Martijn Beudel, Ludvic Zrinzo, Thomas Foltynie, Patricia Limousin, Marwan Hariz, et al. Bilateral adaptive deep brain stimulation is effective in Parkinson's disease. Neurosurg Psychiatry 2016;87:717-721. Epub;2015
3. CONSORT 2010 statement: extension to randomised crossover trials. BMJ 2019; 366:l4378

10. Appendix A

For each subject, two weeks prior to each adjustment visit will be used for this analysis. Data will be provided for aDBS treatment phase 1 and follow-up phase. The following data from JSON, BrainSense and Apple Watch will be provided from Rune Labs.

Source	Parameter	Value/ Category	Description
OC	ID	XXX	the patient ID will be as from OC
	Phase	1/2	1= aDBS treatment phase 2 = follow-up phase
	Next Visit	1/2/3/4/5/6	
Percept data	Group	A/B/C/D	
	N hours available within 2 weeks prior to the visit	Number	
	Sensor contacts (L, R)	Categorical	(0-3, 0-2, 1-3, etc..)
	LFP Power (L, R)	Number	mean, std, min, q1, median, q3, max
	Lower LFP Threshold (L, R)	Number	
	Upper LFP Threshold (L, R)	Number	
	Measured Lower LFP (L, R)	Categorical	
	Measured Upper LFP (L, R)	Categorical	
	DBS Mode	Categorical	aDBS, cDBS
	Stim Electrodes (L, R)	Categorical	
	TEED	Number	mean, std, min, q1, median, q3, max
	Use of event markers	Categorical	
	Time spent below the thresholds (L, R)	%time	
	Time spent between thresholds (L, R)	%time	
	Time spent above thresholds (L, R)	%time	
Apple Watch Data	Dyskinesia Probability AUC	Number	AUC (Area Under the Curve)
	Dyskinesia % time	%time	with Probability ≥20%, 30%, 40%, 50%
	Tremor Probability AUC	Number	AUC (Area Under the Curve)
	Tremor % time	%time	with Probability ≥20%, 30%, 40%, 50%
	Medication Cycle	On/off
